3.1 Overall study design

This is a non-randomized phase II study with RAD001 as first or second line treatment in patients who are either newly diagnosed with radioiodine refractory thyroid cancer or have progressed after chemotherapy with doxorubicine or a small molecule tyrosine kinase inhibitor such as Sorafenib and who have documented disease progression within 6 months.

Similar to prior studies in patients with thyroid cancer, all histologic thyroid cancer types will be included in this trial. While there may be differences in response to treatment between tumor types, this trial will provide an overview about responsiveness to therapy in this rare disease.

Our trial will follow a 2 step design according to Fleming's procedure³³. In the first step, 18 patients with differentiated thyroid cancer (excluding medullary or anaplastic thyroid cancer) and documented disease progression within 6 months will be enrolled. Then a PFS of 6 months or more will be required in at least two patients in order to proceed with the enrollment of 15 more patients for the study to complete its accrual of 33 patients. The time interval of 6 months is chosen because documented disease progression within 6 months is a

requirement for enrollment in this trial. Imaging studies will be obtained every 2 months and if no progression can be demonstrated at the 6 month time point while on therapy, anti-tumor activity is likely. If there is only one or no case of PFS of at least 6 months in the first cohort, the drug combination will be considered ineffective and the trial will be terminated.

In addition, two separate exploratory cohorts will be included in the trial but will not be part of the statistical analysis of the 2 step study. These cohorts include up to 10 patients with medullary thyroid cancer and up to 7 patients with anaplastic thyroid cancer, respectively. These cohorts will be evaluated by descriptive statistics and will provide an initial measure of efficacy in this disease in which no approved and effective treatment options exist. This brings the total number of subjects in this trial to 50.

The patients will be followed for a maximum duration of 24 months. Please see Section 3.4.1.3 for an outline of data that will be collected post 24 months for patient continuing on treatment without progression of disease.

3.2 Study population

3.2.1 Patient population

This is a non-randomized phase II study with RAD001 as first or second line treatment in patients who are either newly diagnosed with radioiodine refractory thyroid cancer or have progressed after chemotherapy with doxorubicine or a small molecule tyrosine kinase inhibitor such as Sorafenib and who have documented disease progression within 6 months during the year prior to protocol treatment with RAD001. The patient must not have had any treatment between the date of progression and the start date of RAD001 treatment, unless discussed with the PI. In selected cases therapy with RAD001 as third or fourth line therapy will be allowed for example if the patient had received sequential therapy with tyrosine kinase inhibitors and chemotherapy that does not contain mTOR inhibitors as part of the regimen.

3.2.2 Inclusion and exclusion criteria

Patients must have baseline evaluations performed prior to the first dose of study drug and must meet all inclusion and exclusion criteria. Results of all baseline evaluations, which assure that all inclusion and exclusion criteria have been satisfied, must be reviewed by the Principal Investigator or his/her designee prior to enrollment of that patient. In addition, the patient must be thoroughly informed about all aspects of the study, including the study visit schedule and required evaluations and all regulatory requirements for informed consent. The written informed consent must be obtained from the patient prior to enrollment. The following criteria apply to all patients enrolled onto the study unless otherwise specified.

Inclusion criteria

- Histologically confirmed locally advanced or metastatic thyroid cancer, excluding thyroid lymphomas not amenable to or refractory to surgical resection, external beam radiotherapy, radioiodine or other local therapies.
- Medullary thyroid cancer with documented evidence of disease progression by modified RECIST³⁴ within 6 months during the year prior to study day 1 (see Appendix A) or symptomatic disease (ie, medullary thyroid cancer-related diarrhea and /or flushing episodes) at the time of screening in the absence of documented disease progression. The patient must not have had any treatment between the date of progression and the start date of RAD001 treatment, unless discussed with the PI.
- Differentiated thyroid cancer (papillary, follicular with subvariants such as Hurthle cell thyroid cancer) with documented evidence of disease progression by modified RECIST within 6 months during the year prior to study day 1 (details see Appendix A). The patient must not have had any treatment between the date of progression and the start date of RAD001 treatment, unless discussed with the PI.
- Anaplastic thyroid cancer with disease progression with documented disease progression by modified RECIST within 6 months during the year prior to study day 1. The patient must not have had any treatment between the date of progression and the start date of RAD001 treatment, unless discussed with the PI.
- Patients must have at least one measurable site of disease according to RECIST criteria that has not been previously irradiated. If the patient has had previous radiation to the marker lesion(s), there must be evidence of progression since the radiation
- Age \geq 18 years
- ECOG performance status \leq 2
- Adequate bone marrow function as shown by: ANC \geq 1.5×10^9 /L, Platelets \geq 100×10^9 /L, Hb $>$ 9 g/dL
- Adequate liver function as shown by:
 - serum bilirubin \leq 1.5 x ULN
 - INR $<$ 1.3 (or $<$ 3 on anticoagulants)
 - ALT and AST \leq 2.5x ULN (\leq 5x ULN in patients with liver metastases)
- Adequate renal function: serum creatinine \leq 1.5 x ULN
- Fasting serum cholesterol \leq 300 mg/dL OR \leq 7.75 mmol/L AND fasting triglycerides \leq 2.5 x ULN. NOTE: In case one or both of these thresholds are exceeded, the patient can only be included after initiation of appropriate lipid lowering medication.
- Signed informed consent

Exclusion criteria

- Patients receiving anticancer therapies within last 2 weeks or who have received radiation therapy within 3 weeks of study day 1
- Patients, who have had a major surgery or significant traumatic injury within 4 weeks of start of study drug, patients who have not recovered from the side effects of any

major surgery (defined as requiring general anesthesia) or patients that may require major surgery during the course of the study

- Prior treatment with any investigational drug within the preceding 3 weeks
- Patients receiving chronic, systemic treatment with corticosteroids or another immunosuppressive agent. Topical or inhaled corticosteroids are allowed.
- Patients should not receive immunization with attenuated live vaccines within 2 weeks of study entry or during study period
- Patients who have brain or leptomeningeal metastases that can not be controlled with radiotherapy or radioiodine treatment including patients who require glucocorticoids for brain or leptomeningeal metastases.
- Other malignancies within the past 3 years except for adequately treated carcinoma of the cervix or basal or squamous cell carcinomas of the skin. Exceptions may be made by the PI for other low risk cancer diagnosis within the last 3 years.
- Patients who have any severe and/or uncontrolled medical conditions or other conditions that could affect their participation in the study such as:
 - Symptomatic congestive heart failure of New York heart Association Class III or IV
 - unstable angina pectoris, symptomatic congestive heart failure, myocardial infarction within 6 months of start of study drug, serious uncontrolled cardiac arrhythmia or any other clinically significant cardiac disease
 - severely impaired lung function
 - uncontrolled diabetes as defined by fasting serum glucose $>1.5 \times$ ULN
 - active (acute or chronic) or uncontrolled severe infections
 - liver disease such as cirrhosis, chronic active hepatitis, chronic persistent hepatitis
 - positive screening hepatitis C test or history of HCV infection including those with a negative viral load test at baseline
- A known history of HIV seropositivity
- Impairment of gastrointestinal function or gastrointestinal disease that may significantly alter the absorption of RAD001 (e.g., ulcerative disease, uncontrolled nausea, vomiting, malabsorption syndrome or small bowel resection)
- Patients with an active, bleeding diathesis
- Female patients who are pregnant or breast feeding, or adults of reproductive potential who are not using effective birth control methods. If barrier contraceptives are being used, these must be continued throughout the trial by both sexes. Hormonal contraceptives are not acceptable as a sole method of contraception. (Women of childbearing potential must have a negative urine or serum pregnancy test within 14 days prior to administration of RAD001)
- Patients who have received prior treatment with an mTOR inhibitor (sirolimus, temsirolimus, everolimus).

- Patients with a known hypersensitivity to RAD001 (everolimus) or other rapamycins (sirolimus, temsirolimus) or to its excipients
- History of noncompliance to medical regimens
- Patients unwilling to or unable to comply with the protocol

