Patients who test positive for a past or active Hepatitis B infection should be given prophylactic administration. If the patient has a positive Hepatitis B test result, they should be treated with Hepatitis B anti-viral lamivudine 100 mg prior to start of RAD001 therapy and throughout the treatment period with RAD001. Some associated toxicities to the lamivudine may include headache, diarrhea, and rash. If the patient needs to be treated with lamivudine, the cost of the treatment will be charged to the patient's insurance. For guidance on management of Hepatitis B and C reactivation, refer to Section 3.2.6.4.

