3.2.6.4 Management of Hepatitis B or C Reactivation

Monitoring and prophylactic treatment for hepatitis B reactivation

Table 3-2 provides details of monitoring and prophylactic therapy according to the baseline results of viral load and serologic markers testing.

Table 3-2 Action to be taken for positive baseline hepatitis B results

Test	Result	Result	Result	Result	Result
HBV-DNA	+	+ or -	-	-	-
HBsAg	+ or -	+	-	-	-
HBs Ab	+ or -	+ or -	+	+ or -	- or + with prior HBV vaccination
HBc Ab	+ or -	+ or -	+ or -	+	-
Recommendation	Prophylaxis treatment should be started 1-2 weeks prior to first dose of study drug Monitor HBV-DNA approximately every 6 weeks		No prophylaxis Monitor HBV-DNA approximately every 3 weeks		No specific action

Antiviral prophylaxis therapy should continue for at least 4 weeks after last dose of study drug. For patients who have already received study drug prior to the approval of the amendment, the same process should be followed at the patient's next visit. The first HBV-DNA result would be regarded as baseline. For hepatitis B reactivation, definition and management guidelines, see Table 3-3 Guidelines for management of hepatitis B.

Table 3-3 Guidelines for management of hepatitis B

HBV reactivation (with or without clinical signs and symptoms)*	
For patients with baseline results: Positive HBV-DNA OR positive HBsAg ----- reactivation is defined as: [Increase of 1 log in HBV-DNA relative to baseline HBV-DNA value OR new appearance of measurable HBV-DNA]	Treat: Start a second antiviral AND Interrupt study drug administration until resolution: ≤ baseline HBV-DNA levels If resolution occurs within ≤ 28 days, study drug should be re-started at one dose lower, if available. If the patient is already receiving the lowest dose of study drug according to the protocol, the patient should restart at the same dose after resolution. Both antiviral therapies should continue at least 4 weeks after last dose of study drug. If resolution occurs > 28 days, patients should discontinue study drug but continue both antiviral therapies at least 4 weeks after last dose of study drug.

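### The eligibility exclusions and the hepatitis B management sections can be read to give opposite answers for patients with active or chronic hepatitis B, and the prophylaxis rules for past infection also conflict

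*Combined protocol and SAP*

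**What the plan says.** Section 3.2.2 has a general exclusion, "Patients who have any severe and/or uncontrolled medical conditions or other conditions that could affect their participation in the study such as", followed by a list of examples. Three of them matter here:

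- The example on the liver reads "liver disease such as cirrhosis, chronic active hepatitis, chronic persistent hepatitis".
- The example on infection, which stands just before it, reads "active (acute or chronic) or uncontrolled severe infections".
- A further example bars anyone who screens positive for hepatitis C or has had it before, even with no detectable virus at baseline.

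Hepatitis C is therefore excluded by name. Hepatitis B is not mentioned in the list, either as excluded or as excepted.

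Section 3.2.5j states: "Patients who test positive for a past or active Hepatitis B infection should be given prophylactic administration". Of patients with a positive hepatitis B test it says "they should be treated with Hepatitis B anti-viral lamivudine 100 mg prior to start of RAD001 therapy and throughout the treatment period with RAD001".

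In Section 3.2.6.4, Table 3-2 says of patients positive at baseline for HBV-DNA or HBsAg: "Prophylaxis treatment should be started 1-2 weeks prior to first dose of study drug". For patients negative on both but positive for hepatitis B antibodies other than through vaccination, it gives no prophylaxis and asks for HBV-DNA monitoring. Table 3-3 then sets rules for reactivation on study drug, with one row headed "For patients with baseline results: Positive HBV-DNA OR positive HBsAg".

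Footnote 3 to the visit schedule (Table 3.4a) repeats the plan of an antiviral followed by study drug for HBV-DNA-positive or HBsAg-positive patients. It calls only hepatitis C patients ineligible.

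**The concern.** The same word, active, describes a chronic infection that 3.2.2 keeps out and a hepatitis B infection that 3.2.5j prepares for dosing. The liver-disease example in 3.2.2 adds two forms of chronic hepatitis without saying whether hepatitis B is meant.

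Safety is at stake first. Section 3.2.5j reports hepatitis B reactivation on everolimus and links reactivation to morbidity and mortality. Table 3-3 records it as grade 3, or grade 4 if life-threatening, and interrupts the drug. Whether a patient with active hepatitis B receives the drug at all should not turn on which section is read first.

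Consistency comes second. Section 3.2.2 requires every criterion to be met, and Appendix D, Section 8.1 classes enrolment of a patient who fails a criterion as a protocol exception. The same patient could be properly enrolled on one reading and an exception on the other.

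**Working it through.** No arithmetic applies. The check sets the sections side by side by baseline result.

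| Baseline finding | 3.2.2 | 3.2.5j | Table 3-2 | Table 3-3 | Footnote 3 |
|---|---|---|---|---|---|
| HBV-DNA or HBsAg positive, judged active or chronic hepatitis B | Can be read to exclude | Antiviral, then RAD001 | Antiviral before first dose | On-drug rules | Antiviral, then study drug |
| HBV-DNA or HBsAg positive, no liver disease and not judged an active infection | No example clearly applies | Antiviral, then RAD001 | Antiviral before first dose | On-drug rules | Antiviral, then study drug |
| Antibodies only (past infection) | No example clearly applies | Prophylaxis | No prophylaxis; monitor | First antiviral started at reactivation | Antiviral advice names only HBV-DNA or HBsAg positives |
| Hepatitis C positive or past | Excluded by name | – | – | – | Ineligible |

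1. **First row: the eligibility conflict.** 3.2.2 can be read to exclude, while the other four places lead to dosing. No section says which governs.

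2. **Is Table 3-2 only for patients already on the drug?** No. It times prophylaxis from the first dose, and a separate sentence deals with patients who had received study drug before the amendment.

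3. **Do definitions settle it?** No. Neither hepatitis term in 3.2.2 is defined, and neither is tied to HBV-DNA, HBsAg or ALT. The only numerical liver limits are the general ones for bilirubin, INR and ALT/AST among the inclusion criteria.

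4. **Second row: no clear conflict.** A positive blood test is not in itself liver disease, so 3.2.2 and Table 3-2 can be applied in turn.

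5. **Third row: the prophylaxis conflict.** 3.2.5j covers past as well as active infection. Table 3-2 withholds prophylaxis from antibody-only patients, and Table 3-3 agrees with Table 3-2 by treating an antiviral begun at reactivation as their first.

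6. **Link to the statistics.** The design in Section 7.1 (33 patients, success at 7 or more, alpha 0.092, power 0.970, rates 0.12 and 0.35) takes no input from hepatitis B status.

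**The case against.** There is a serious case that the text is workable as it stands.

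- **The parent clause.** Both exclusions are examples under a clause about severe or uncontrolled conditions, and in the infection example the word severe may qualify the whole phrase. This weakens the bar without removing it: the clause also covers other conditions that could affect participation, and the liver-disease example stands separately.
- **Hepatitis C is named and hepatitis B is not.** Hepatitis C is excluded in 3.2.2, 3.2.6.4 and footnote 3, and footnote 3 sets out hepatitis B pre-treatment in the same note. The natural inference is that hepatitis B positivity alone does not exclude. That inference is reasonable, but it does not say what happens when the positive result reflects active or chronic hepatitis.
- **Central review.** The Principal Investigator or a designee reviews baseline results (3.2.2), the Lead Institution verifies eligibility from source documents (Appendix D, 5.7), and no exception is made without IRB approval (Appendix D, 5.9.2). One body can therefore apply one reading. It has no written rule to apply, however, and the laboratory reports listed in Appendix D, 5.7 do not name the hepatitis tests.

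A reader might also infer more than the documents support. It is tempting to say that every HBV-DNA-positive or HBsAg-positive candidate is caught, or that sites have no means of deciding. The second row of the table and the central review tell against both. Nor can a viraemic patient with modestly raised ALT be declared excluded: calling that chronic active hepatitis needs a definition the protocol does not give.

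**Conclusion.** The point holds as an internal contradiction that bears on safety and should be corrected. It has two parts: eligibility is undetermined for patients whose positive result reflects active or chronic hepatitis B, and the instructions on prophylaxis for past infection disagree.

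Its size cannot be given. The documents state no prevalence of hepatitis B, so the number of patients affected is unknown. Alpha, power and sample size are untouched.

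A reader might infer that reactivation turns such patients into failures for the primary endpoint. The documents do not support that as a general consequence. Section 3.4.1.3 keeps patients who stop treatment without progression under follow-up for progression, and Section 7.1 counts as failures those who drop out before the 6-month evaluation. Stopping the drug is not in itself dropping out.

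The conclusion assumes that at least some hepatitis B that 3.2.5j would call active also falls within the infection or liver-disease examples of 3.2.2. The wording allows this, and nothing in the protocol rules it out.

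**What to change.** Add one hepatitis B line to Section 3.2.2, as is already done for hepatitis C, stating how the infection and liver-disease exclusions apply to patients with positive hepatitis B results. Then align Section 3.2.5j, Tables 3-2 and 3-3 and footnote 3 with it, including whether past infection shown only by antibodies calls for prophylaxis. Which patients may enter and who receives an antiviral are clinical decisions for the sponsor; the statistical review asks only that the sections give one answer.

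The cost is one eligibility line and a few aligned sentences. Because it touches eligibility criteria, Appendix D, Section 5.4 would class it as a major amendment needing full IRB approval. No new test is needed, since the hepatitis B markers and liver enzymes are already collected at screening.

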3.2.3 Interruption or discontinuation of treatment

For patients who are unable to tolerate the protocol-specified dosing schedule, dose adjustments are permitted in order to keep the patient on study drug. Patients may be re-escalated back to the previous dose if he/she is stable, his/her symptoms are related to disease and not treatment, and you receive the PI's permission. If administration of RAD001 must be interrupted because of unacceptable toxicity, drug dosing will be interrupted or modified according to rules described in Table 3-1. Toxicity will be assessed using the NIH-NCI Common Terminology Criteria for Adverse Events, version 3.0 (CTCAEv3.0, (<http://ctep.cancer.gov/forms/CTCAEv3.pdf>)).

Table 3.0 RAD001 dose level modification guidelines

Dose level	Dose and schedule
0 (starting dose)	10 mg po daily
-1	5 mg po daily
-2	5 mg po every other day

If patients are unable to tolerate dose level -2, the patient will come off study.

Table 3-1 Criteria for dose-modification in case of suspected RAD001 toxicity and re-initiation of RAD001 treatment

Toxicity	Actions
Non-hematological toxicity	
Grade 2 (except pneumonitis – refer to Table 3-2a)	If the toxicity is tolerable to the patient, maintain the same dose. If the toxicity is intolerable to patient, interrupt RAD001 until recovery to grade ≤ 1 . Then reintroduce RAD001 at same dose. If event returns to grade 2, then interrupt RAD001 until recovery to grade ≤ 1 . Then reintroduce RAD001 at the lower dose level.
Grade 3 (except hyperlipidemia*) (except pneumonitis – refer to Table 3-2a)	Interrupt RAD001 until recovery to grade ≤ 1 . Then reintroduce RAD001 at the lower dose level. For pneumonitis consider the use of a short course of corticosteroids.
Grade 4 (except hyperlipidemia*)	Discontinue RAD001.
Hematological toxicity	
Grade 2 Thrombocytopenia (platelets $<75, \geq 50 \times 10^9/L$)	Interrupt RAD001 until recovery to grade ≤ 1 ($>75 \times 10^9/L$). Then reintroduce RAD001 at initial dose. If thrombocytopenia again returns to grade 2, interrupt RAD001 until recovery to grade ≤ 1 . Then reintroduce RAD001 at the lower dose level.
Grade 3 Thrombocytopenia (platelets $<50, \geq 25 \times 10^9/L$)	Interrupt RAD001 until recovery to grade ≤ 1 (platelets $\geq 75 \times 10^9/L$). Then resume RAD001 at one dose level lower. If grade 3 thrombocytopenia recurs, discontinue RAD001.
Grade 4 Thrombocytopenia (platelets $< 25 \times 10^9/L$)	Discontinue RAD001.
Grade 3 Neutropenia (neutrophils $<1, \geq 0.5 \times 10^9/L$)	Interrupt RAD001 until recovery to grade ≤ 1 (neutrophils $\geq 1.5 \times 10^9/L$). Then resume RAD001 at the initial dose. If ANC again returns to Grade 3, hold RAD001 until the ANC $\geq 1.5 \times 10^9/L$. Then resume RAD001 dosing at the lower dose level. Discontinue patient from study therapy for a third episode of grade 3 neutropenia.
Grade 4 Neutropenia (neutrophils $< 0.5 \times 10^9/L$)	Interrupt RAD001 until recovery to grade ≤ 1 (neutrophils $\geq 1.5 \times 10^9/L$). Then resume RAD001 at the lower dose level. If grade 3 or grade 4 neutropenia occurs despite this dose reduction, discontinue RAD001.
Grade 3 febrile neutropenia (not life-threatening)	Interrupt RAD001 until resolution of fever and neutropenia to grade ≤ 1 . Hold further RAD001 until the ANC $\geq 1,500/mm^3$ and fever has resolved. Then resume RAD001 at the lower dose level. If febrile neutropenia recurs, discontinue RAD001.
Grade 4 febrile neutropenia (life-threatening)	Discontinue RAD001.
Any hematological or non-hematological toxicity requiring interruption for ≥ 3 weeks	Discontinue RAD001

*Grade 3 or higher hyperlipidemia (hypercholesterolemia and/or hypertriglyceridemia) should be managed using medical therapies (see Sec. 3.2.6.2).

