3.2.4 Monitoring of RAD001 suspected toxicities

Patients whose treatment is interrupted or permanently discontinued due to an adverse event or abnormal laboratory value suspected to be related to RAD001 must be followed at least weekly until the adverse event or abnormal laboratory resolves or returns to grade 1. If a patient requires a dose delay of > 21 days from the intended day of the next scheduled dose, then the patient must be discontinued from the study.

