pneumonitis was reported for a patient with metastatic infiltrating ductal carcinoma of the breast treated with 10 mg/day, which developed approximately two months after starting RAD001. Cytology for both the pleural and pericardial fluids were positive for malignancy. The death was considered possibly related to the underlying late stage tumor and study drug. Additionally, one patient treated with 10 mg/day died due to severe acute respiratory distress syndrome and septic shock. Thoracic CT scan demonstrated condensation in the majority of the left lower lobe and frosted glass appearance in the left upper lobe, lingula, and right lung.

Along with the cases of non-infectious pneumonitis, serious opportunistic infections have also been reported in cancer patients treated with RAD001: mycobacterium, aspergillus, and fatal candidal sepsis, and fatal pneumocystis carinii in particular. Because RAD001, as other rapamycins, inhibits proliferation of activated lymphocytes and reduces neutrophil counts, treatment with RAD001 must be considered as predisposing patients to the risk of infection. This risk will be higher in patients severely immunocompromised because of their underlying disease and/or co-medications. Outcome may be fatal in case of serious infections.

3.2.5e Pericardial effusions, pleural effusions, and weight loss have been reported as serious adverse events with suspected causality. Due to the imprecision of causality assessments it should not be assumed that all of these events are indeed the result of therapy with everolimus since confounding factors are present relating mainly to complications of the underlying disease and to the use of concomitant medications.

3.2.5f A reduction in blood cell counts is frequent when RAD001 therapy is initiated. Without clinical significance and infrequently, anemia and thrombocytopenia have been reported. In heavily pretreated patients with aggressive lymphoma, the incidence of grade 3 anemia, neutropenia, and thrombocytopenia was reported to be 11%, 16%, and 30%, respectively. Serious, suspected drug-related hemorrhages have been exceptional. Nevertheless, RAD001 should be considered as predisposing patients to hemorrhage, potentially fatal, should they develop severe drug-related thrombocytopenia.

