3.2.5g Discrete, reversible changes in liver enzymes have been found to occur in numerous patients during treatment with RAD001 in oncology clinical studies, and in a study in rheumatoid arthritis. In oncology studies, these changes may be evident only in patients without severe underlying morbidity. The increase in transaminase's (AST and ALT) generally appears after 4 weeks of treatment. In all but a few cases it does not exceed Grade 1 ($\leq 2.5 \times \text{ULN}$). Similarly, mild increases in alkaline phosphatases can coexist. Spontaneous corrections or intermittent correction with continued treatment can occur. Serum bilirubin is not increased. In studies of patients with advanced cancers, clinically relevant changes in liver enzymes have been invariably associated with the presence of liver metastases and/or progression of the underlying cancer.

3.2.5h Renal failure has been reported in five suspected cases to date. One patient with no alternative explanation made a complete recovery following study drug adjustment and no treatment/therapy for the event. The rest of the patients had concurrent morbidities, which might have contributed to the reported events.

3.2.5i Hypophosphatemia, hypomagnesemia, hyponatremia and hypocalcemia have been reported as serious adverse reactions. Electrolytes should be monitored in patients treated with RAD001.

Table 3-1 provides general recommendations for the management of patients, with suspected drug toxicities while on treatment with RAD001 as single-agent therapy.

More detailed information regarding RAD001 reported suspected toxicities and individual cases is provided in the [Investigator's Brochure].

3.2.5j Reactivation of Hepatitis B (HBV) has been observed in sporadic cases with patients in this setting with everolimus. Use of antivirals during anti-cancer therapy has been shown to reduce the risk of Hepatitis B virus reactivation and associated morbidity and mortality. A detailed assessment of Hepatitis B/C medical history and risk factors must be done for all patients at screening, with testing performed prior to the first dose of everolimus.

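### Read literally, Table 3-1 stops RAD001 for a third grade 3 neutropenia episode but lets a first grade 4 episode at the same point resume treatment

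*Combined protocol and SAP*

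**What the plan says.** Section 3.2.3 presents Table 3-1 as governing toxicity management: "drug dosing will be interrupted or modified according to rules described in Table 3-1". Section 3.2.5i is softer: "Table 3-1 provides general recommendations for the management of patients". Neither section alters the neutropenia rows, which read as follows.

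- **Grade 3** (neutrophils 0.5 to below 1 × 10⁹/L). After the first episode, interrupt and resume at the initial dose. After the second, hold and resume at the lower dose level. Then: "Discontinue patient from study therapy for a third episode of grade 3 neutropenia".
- **Grade 4** (neutrophils below 0.5 × 10⁹/L). Interrupt and resume at the lower dose level. Then: "If grade 3 or grade 4 neutropenia occurs despite this dose reduction, discontinue RAD001".

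Table 3.0 sets the levels: 0 is 10 mg daily, -1 is 5 mg daily, -2 is 5 mg every other day. Below that there is nothing: "If patients are unable to tolerate dose level -2, the patient will come off study". Febrile neutropenia has its own rows, and any toxicity that needs an interruption of 3 weeks or more ends RAD001.

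**The concern.** A stopping rule should be at least as strict for the worse event. The two afebrile rows each count only their own history. The grade 3 row counts grade 3 episodes, and the stop clause of the grade 4 row looks back to a reduction that the same row has just ordered. A patient who moves from one row to the other can therefore lose the benefit of a stop that was already due.

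The stake is patient safety. Section 3.2.5d warns that the drug "reduces neutrophil counts, treatment with RAD001 must be considered as predisposing patients to the risk of infection", and adds that serious infection can be fatal. Elsewhere in Table 3-1, every toxicity type with both a grade 3 and a grade 4 row stops at grade 4, hyperlipidemia excepted. Sites outside the lead center use the same table, so an intention that is not written down may be applied differently from site to site.

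**Working it through.** The plan states no figure on this point, so the check is a trace of the two rows.

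**Inputs.** The grade 3 and grade 4 neutropenia rows of Table 3-1 and the dose levels of Table 3.0. Start at level 0. Assume afebrile episodes only, each recovering in under 3 weeks, with no reduction for another toxicity and no re-escalation. A history ends at the first stop.

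| Episodes, in order of grade | Action as printed |
|---|---|
| 3 | resume at 0 |
| 4 | resume at -1 |
| 3-3 | resume at -1 |
| 3-4 | resume at -1 |
| 4-3 | stop |
| 4-4 | stop |
| 3-3-3 | stop |
| **3-3-4** | **resume** |
| 3-4-3 | stop |
| 3-4-4 | stop |

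Reachable histories: 2 + 4 + 4 = 10. In nine of them, changing the last episode from grade 3 to grade 4 never earns a more lenient action. The exception is 3-3-4: the same patient at the same dose stops for grade 3 and resumes for grade 4. Order matters too, since 3-4-3 stops and 3-3-4 does not.

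**Which row applies to the third episode in 3-3-4?** A count below 0.5 lies outside the grade 3 row's range, so the printed third-episode rule does not match it. It is the first grade 4 episode, so the grade 4 row has made no earlier reduction for its stop clause to refer to. What remains is interrupt and resume.

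**At what dose?** The neutropenia rows do not tie the lower dose level to the patient's current dose, whereas the grade 3 thrombocytopenia row specifies a drop of one level.

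- If it means one step below the current dose: -1 to -2, that is, 5 mg every other day.
- If it means level -1: the patient resumes at 5 mg daily, unchanged.

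Neither reading is a stop.

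**Proposed rule** (stop at a third episode of grade 3 or grade 4). Of the four three-episode histories, 3-3-3, 3-4-3 and 3-4-4 already stop, and 3-3-4 changes from resume to stop. The six shorter histories are untouched. Histories changed: 1 of 10.

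**The case against.** The best reply is that a sensible investigator would stop anyway. Both rows use the same term for the reduced dose, so a patient already at that dose because of neutropenia who then reaches grade 4 can naturally be seen as failing despite the reduction. Alternatively, a grade 4 event can be counted as the third episode. Either reading removes the inversion, and either may be what the sponsor meant. But neither is written. The reference to the reduction directly follows the one ordered in the same row. And the grade 4 row names both grades where both are meant, while the third-episode clause names only grade 3.

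It is also fair to say that the consequence is small. The sequence needs two recovered grade 3 episodes and then an afebrile grade 4 episode that recovers in under 3 weeks, in a trial of 50. Sections 1.1.3.3 and 3.2.5 say that infections have not been notably frequent or severe. Patients whose dosing is interrupted "must be followed at least weekly until the adverse event or abnormal laboratory resolves or returns to grade 1", and Section 3.4.5 lists all grade 4 events for IRB reporting. These points stand. They make an unexamined restart less likely, but they do not state the dosing action.

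A reader might infer that the inversion also arises at level 0, after re-escalation, because "Patients may be re-escalated back to the previous dose if he/she is stable". The documents do not support that. The same sentence also requires symptoms to be due to disease rather than treatment, plus the PI's permission. A reduction under Table 3-1 is for suspected RAD001 toxicity, so that condition is not met. At level -2 there is no lower dose, so the patient comes off study and no inversion arises.

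**Conclusion.** The point holds for one sequence: two grade 3 episodes, reduction to level -1, then a first afebrile grade 4 episode. As printed, the more severe event receives the more lenient action. That is 1 of 10 reachable histories, on the assumptions listed in the working. The documents give no rate for repeated or mixed-grade neutropenia, so no number of affected patients can be estimated.

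Two broader conclusions would go too far. Table 3-1 is not generally lax about grade 4 neutropenia: a first grade 4 episode brings an immediate reduction, where a first grade 3 episode does not, and the next grade 3 or grade 4 episode stops the drug. Nor can resumption at level -2 be stated as fact, since it is one of two readings. This is a gap in the wording of a safety rule that merits correction. It does not touch alpha, power or sample size.

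**What to change.** In the grade 3 neutropenia row, widen the last clause so that RAD001 stops for a third neutropenia episode of grade 3 or grade 4. In the grade 4 row, add that this stop takes precedence over resumption. Leave the febrile neutropenia rows as they are. Counting episodes is safer than writing a stop after any earlier neutropenia reduction, because that wording could also capture reductions made under the febrile rows. The sponsor should say whether a febrile episode counts toward the three, since the 10 histories cover afebrile episodes only.

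The cost is a short wording change to two table rows in an amendment, with no added assessments. A first grade 4 episode and the 3-4 sequence keep their present action. The downside is that a rare patient loses one further resumption. If the sponsor always meant to stop, the change only records that.
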